4. STUDY DESIGN

4.1 General Design

A summary of the study will be presented here; full details are provided in the protocol. This is a randomized, single-blind, placebo-controlled, parallel-group, multicentre study in subjects with CAD. For full details please refer to section 1.4 of the protocol.

4.2 Discussion of Study Design

A randomized, blinded, parallel-group, multicentre, placebo-controlled study design is standard in Proof-of-Principle studies and is considered the best design to achieve the objectives of the study, from both safety and efficacy perspectives. Full details regarding the rationale for study design, doses and control groups are reported in section 1.2 of the protocol.

4.3 Method of Assignment of Subjects to Treatment Groups

A centralized (IRT) randomization schedule will be generated by using the AstraZeneca randomization solution (AZRand). Subjects will be randomized in a ratio 2:1:2 to receive either AZD5718 AZD5718 Or Placebo. At randomization the IRT will assign eligible subjects a unique randomization code and blinded *Distribution:* Original: Copy:

Sponsor:	AstraZeneca AB	Protocol/CIP Number:	D7550C00003
CIL Project Number:	40343		

The randomization will be stratified with type of Myocardial Infarction (MI) as a factor (STEMI vs NSTEMI).

4.4 Blinding

The study will have a single blind design. The study is single-blind regarding treatment strengths, but double blind in terms of active or placebo.

No member of the study team at AstraZeneca, or representative, personnel at study centres, or any Clinical Research Organization (CRO) handling data will have access to the randomization scheme during the conduct of the study, with the exception of the Informatics personnel generating the randomization scheme as well as AstraZeneca Supply Chain, and the CRO companies conducting PK sample analyses, providing the IRT and carrying out the packaging and labelling of the study medication. This documentation will be kept in a secure location until the end of the study.

Individual treatment codes, indicating the treatment randomization for each randomized subject, will be available to the Investigator(s) or pharmacists from the IRT. The treatment code should not be broken except in medical emergencies when the appropriate management of the subject requires knowledge of the treatment randomization. The Investigator documents and reports the action to AstraZeneca, without revealing the treatment given to the subject to the AstraZeneca staff.

AstraZeneca retains the right to break the code for Serious Adverse Events (SAEs) that are unexpected and are suspected to be causally related to an IP and that potentially require expedited reporting to regulatory authorities.

Treatment codes will not be broken for the planned analyses of data until all decisions on the evaluability of the data from each individual subject have been made and documented. For the interim analysis, independent personnel with no other involvement in the study will be unblinded to certain data. The process for the conduct of the interim analysis including the unblinding process will be described in a separate interim analysis plan.

4.5 Determination of Sample Size

The study has been powered to show a statistically significant result for the primary endpoint, first, second and third secondary endpoints. To preserve the overall type1-error at 5% when testing these four endpoints a Hierarchical Procedures will be used (Dmitrienko A et al 2006). This procedure implies that one will test the four endpoints in a predefined sequence: test of main objective, test of first secondary objective, test of second secondary objective, test of third secondary objective. The test procedure will stop as soon as the first

Distribution:	Original:	
TPCA025 Version 2		
(based on TPQA036 Version 2)		
CONFIDENTIAL AND PROPRIETARY	Page 15 of 80	

Effective Date: 27th August 2017 Prior Effective Date: 21st December 2016

Copy:

Sponsor:	AstraZeneca AB	Protocol/CIP Number:	D7550C00003
CIL Project Number:	40343		

none-significant test, one-sided test at a 5% level, occur and all following test will be declared as none-significant.

The Hierarchical testing sequence for the four endpoints are:

- 1. Change from baseline in Creatinine-normalized u-LTE4 at 4 weeks
- 2. Change from baseline in Creatinine-normalized u-LTE₄ at 12 weeks
- 3. Change from baseline in CFVR at 12 weeks
- 4. Change from baseline in CFVR at 4 weeks

Data from MAD study shows inhibition of u-LTE₄ by AZD5718 can be assumed to be log-normally distributed, with an expected inhibition of u-LTE₄ of approximately 96% and a standard deviation of <4%. Patients given placebo are expected to have no inhibition of u-LTE₄ with the same standard deviation (on the logarithmic scale) as patients given AZD5718 Given this, 33 evaluable patients in the AZD5718 group and 33 evaluable patients given placebo will be sufficient to achieve > 99% power to show a statistically significant inhibition of u-LTE₄ of at least 80%, using a one-sided confidence interval of 95% at week 12.

Assuming a log-normal distribution of the CFVR and an expected 20% increase in CFVR in the AZD5718 group compared to placebo with a coefficient of variation (CV) of 30%, 33 evaluable patients per arm is required to achieve 80% power with a one-sided confidence interval of 95%.

About 40 randomized patients per arm (AZD5718 per placebo) treated for 12 weeks is needed to account for non-evaluable patients (approximate 18% dropout).

For supporting dose selection in future studies, a treatment arm with about 20 randomized patients receiving AZD5718 for 12 weeks is included in the study, in order to get 17 evaluable patients. The number of 17 subjects has been deemed to provide sufficient exposure-response information.

5. CHANGES IN THE CONDUCT OF THE STUDY OR PLANNED ANALYSES

This SAP is implemented based on CSP v5.0 dated February 11, 2019.

5.1 Changes in the Conduct of the Study

No changes respect to the CSP v5.0 dated February 11, 2019 are present.

5.2 Changes from the Analyses Planned in the Protocol/CIP

• Protocol Section 8.5 states that geometric mean and CV will be presented for all efficacy and safety variables. However, these will be presented only for log-normal variables as deemed not relevant for all the other variables.

Distribution:

Original:

Copy:

Page 16 of 80

Sponsor:	AstraZeneca AB	Protocol/CIP Number:	D7550C00003
CIL Project Number:	40343		

- Protocol section 8.5.3 refers to changes from baseline in Electrocardiogram (ECG) parameters. Only the overall ECG evaluation will be summarised.
- Protocol refers to evaluable subjects as subjects with valid CFVR measurements at Visit 2 (baseline), and one postbaseline visit as judged by the CFVR Core lab. However, CFVR Core lab will flag the validity of the measurements for the single visit. Then, the evaluability of the subject will be stated based on the validity of the 2 measurements, at Visit 2 and at one postbaseline visit.
- Protocol section 8.5.3 states that laboratory data for haematology and clinical chemistry will be summarized by treatment group. The frequency of changes with respect to normal ranges between baseline and end of treatment will be tabulated. However as per standard AZ, the frequency of changes with respect to normal ranges will be tabulated between baseline and worst case registered (minimum or maximum) during treatment.
- Protocol section 8.5.3 states that shifts from normal to abnormal between baseline and end of treatment time point will be evaluated for urinalysis. However as per standard AZ TOC, shifts for urinalysis will be based on the modalities of the variables.
- Protocol section 5.2 stated that Serology (Human immunodeficiency virus (HIV) I and II, Hepatitis B surface Antigen (HBsAg), Hepatitis C virus antibody), and for females only FSH (mIU/ml) and LH (IU/L) will be performed at a local laboratory for screening only. However, these variables are not recorded in the CRF and will not be analysed.
- Protocol section 3.5 stated that IWRS/IVRS will assign eligible patients a unique randomization code and blinded investigational product (IP) kit number(s) to the patient; However, IWRS/IVRS will be replaced with IRT.
- Protocol section 8.3.1 stated that the efficacy analysis set will include all patients who were randomised, received at least one dose of study medication and have at least one baseline or postbaseline measurement. However, here it will have specified that this population will include all patients who were randomised, received at least one dose of study medication and have at least one baseline or postbaseline measurement for at least one of the efficacy variables (including all, primary secondary or exploratory variables).
- Protocol section 8.5.6 stated that an interim analysis plan will be prepared and finalized prior to the first administrative interim analysis. However, this interim analysis plan is based on a dedicated section of the SAP and there will be an update of the interim analysis charter before the second interim analysis.
- Protocol section 8.1 stated that any subsequent amendments to the SAP will be documented, with final amendments completed prior to unblinding of the data for the analysis. But it should be added that unblinded team will not be involved in any SAP amendment which will take place after the first unblinding for the first interim analysis.
- Protocol section 4.1 stated that CFVR measurement should be done before the IP intake during the visit. In the SAP, measurements done 3 days after last dose can be considered as the visit measurement.
- Protocol section 5.3.2 included a brief description of the question SF-36 V1 while V2 is used in the study. The wording was updated in the SAP to be consistent with the questionnaire SF-36 V2.

Distribution:

Original:

Copy:

TPCA025 Version 2 (based on TPQA036 Version 2) CONFIDENTIAL AND PROPRIETARY

Page 17 of 80

Sponsor:	AstraZeneca AB	Protocol/CIP Number:	D7550C00003
CIL Project Number:	40343		

- Protocol section 2.2 stated that standard model population PK parameters would be reported in a separate report. However, plasma concentrations will be part of the CSR and PK parameters described in a separate report.
- Protocol section 4.1 described an on-site Visit 5 (Follow-up). However, due to COVID19 situation, some phone visits replaced on-site visits. Protocol deviations were reported for each patient in that situation.

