2.3 Safety objectives

Safety Objective:	Outcome Measure:
To assess the safety and tolerability of AZD5718 in CAD patients	
 - Adverse Events/Serious Adverse Events (AEs/SAEs) - Vital signs - Clinical chemistry/haematology parameters - Electrocardiogram (ECG) assessments

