5.2.4.1 Resting 12-lead ECG

The following parameters or time intervals will be recorded for each ECG: RR, PR, QRS, QT, QTcF and heart rate (HR).

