8.5.3 Analysis of safety variables

AEs will be summarised by treatment group by means of counts summaries by Medical Dictionary for Regulatory Activities (MedDRA) System Organ Class and Preferred Term (PT). All AEs will be listed and assigned to on/off treatment period as:

- Baseline period: The time before first administration of IP.
- On treatment: The time from first administration of IP until 7 days after last dose of IP.
- Off treatment: More than 7 days after last dose of IP.

AEs will be assigned to the period where they start.

Laboratory data for haematology and clinical chemistry will be summarized by treatment group. The frequency of changes with respect to normal ranges between baseline and end of treatment will be tabulated. Shifts from normal to abnormal between baseline and end of treatment time point will be evaluated for urinalysis. Descriptive statistics might need to be applied to evaluate some of the reported urine laboratory values changes. The incidence of markedly abnormal values and changes from baseline in the ECG parameters will be summarised by treatment group. Categorical outliers may be presented by numbers but need to be considered in context of inclusion/exclusion criteria. Physical examination and vital signs variables will be summarised by treatment group.

Other safety variables will be summarised as appropriate. Further details will be provided in the SAP.

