Vital signs will be obtained at time points indicated in section 6.1 (and ad-hoc as medically indicated). Pulse (beats/minute, radial artery, during 30 seconds) and pulse oximetry (%) will be measured before blood pressure and in a lying position after 10 minutes of rest. Thereafter, systolic and diastolic blood pressure (mmHg, the cuff method on the arm opposite to the one used for blood sampling) will be measured using the same cuff, appropriate for arm circumference, and in the same position, throughout the study. Subjects should be in the same position for the vital signs measurements throughout the study.

Change from baseline to each post-baseline measurement will be calculated as the postbaseline visit value minus the baseline visit value.

Electrocardiogram (ECG)

12-lead ECG recordings will be collected according to the assessments schedule presented in section 6.1. The investigator will make an overall evaluation of the ECG as normal, abnormal, abnormal non-clinically significant and abnormal clinically significant. Abnormal values shall not be recorded as AEs unless deemed clinically significant. Last observation on-treatment used for statistical analyses is the last available value among those in the On-treatment phase. If several measurements are collected on the last date (same day), the last on-treatment value will be the worst of the measurements collected during that day.

Physical Examination

A complete physical examination will be performed at Screening (Visit 1) and at Follow-up (Visit 5) and will include an assessment of the following: general appearance, respiratory, cardiovascular, abdomen, skin, head and neck (including ears, eyes, nose and throat), lymph Distribution: Original:

TPCA025 Version 2 (based on TPQA036 Version 2) Copy:

Effective Date: 27th August 2017 Prior Effective Date: 21st December 2016

Sponsor:	AstraZeneca AB	Protocol/CIP Number:	D7550C00003
CIL Project Number:	40343		

nodes, thyroid, musculoskeletal (including spine and extremities) and neurological systems. On the other occasions (Visits 2, 3, 4 and 4c) a brief physical examination (general appearance, skin, abdomen and musculoskeletal, cardiovascular and respiratory systems) will be conducted. Any new or aggravated clinically relevant abnormal medical finding at a physical examination as compared with the baseline assessment will be reported as an AE.

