7. STATISTICAL METHODS

7.1 General Methodology

Data will be summarized using descriptive statistics, by treatment group which consist of AZD5718 AZD5718 and placebo, where the placebo group matches the loses respectively. Data will be summarized at each visit.

For continuous variables, descriptive statistics will include the number of subjects (n), mean, SD, median, minimum and maximum.

For log-normal variables, descriptive statistics will include n, mean, SD, median, minimum, maximum, geometric mean (GeoMean) and coefficient of variation (CV).

For categorical variables and unless otherwise specified, the number and percentages of subjects by categories will be tabulated. Percentages will be calculated based on the number of subjects with no missing data, i.e., will add up to 100%. Categories with count of zero will be not displayed.

Distribution:

Original:

Copy:

TPCA025 Version 2 (based on TPQA036 Version 2)

Sponsor:	AstraZeneca AB	Protocol/CIP Number:	D7550C00003
CIL Project Number:	40343		

For count variables descriptive statistics will be similar as for continuous variables.

All efficacy, exploratory and safety variables as well as PK plasma concentrations will be summarized by treatment group and at each visit as appropriate using descriptive statistics as above. For continuous variables, descriptive statistics will be summarized both for the observed values and the absolute changes from baseline.

Changes from baseline, in certain categorical variables will be summarized using shift tables. The number and percent of subjects within each treatment group will be generated for each category post-baseline by baseline category.

Decimal points will be presented as follow:

- If the original variable has 1 or less significant decimal points then Mean, Median, first quartile (Q1), third quartile (Q3), GeoMean, LSmean, CI of the LSmean will be rounded to one more decimal point than the original variable significant decimal points
- If the original variable has 2 or more significant decimal points then Mean, Median, first quartile (Q1), third quartile (Q3), GeoMean, LSmean, CI of the LSmean will be rounded to same decimal points than the original variable significant decimal points
- If the original variable has zero significant decimal points then the SD, SE will be rounded to one more decimal point than the mean

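### SAP 5.2 drops the protocol's by-arm summary of ECG interval changes without a reason, and the rating shift that remains uses only the last on-treatment ECG

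*SAP*

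**What the plan says.** ECG is one of the outcome measures for the safety objective (protocol 2.3). Protocol 5.2.4.1 lists six measures to be recorded for each ECG: RR, PR, QRS, QT, QTcF and heart rate. For analysis, protocol 8.5.3 states: "The incidence of markedly abnormal values and changes from baseline in the ECG parameters will be summarised by treatment group". Its next sentence makes counts of categorical outliers optional.

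SAP 5.2 lists this among its departures from the protocol: "Protocol section 8.5.3 refers to changes from baseline in Electrocardiogram (ECG) parameters", followed by "Only the overall ECG evaluation will be summarised". No reason is attached. Several neighbouring bullets do give one: not relevant for the variable type, sponsor standard, or not captured in the CRF.

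SAP 6.6.4 describes the rating: "The investigator will make an overall evaluation of the ECG as normal, abnormal, abnormal non-clinically significant and abnormal clinically significant". It also fixes which ECG is used: "Last observation on-treatment used for statistical analyses is the last available value among those in the On-treatment phase". The worst rating is taken only among ECGs on that last day. SAP 8.8.4 then plans a shift from baseline to that observation, by cohort, and a listing of abnormal findings. Under SAP 7.1 shift tables are by arm: "The number and percent of subjects within each treatment group will be generated for each category post-baseline by baseline category".

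On the liver, SAP 6.6.3 defines a potential Hy's-law case over the whole period after dosing starts and requires the transaminase rise to come first or on the same day as the bilirubin rise. The table itself crosses each patient's highest on-treatment values.

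**The concern.** An overall rating is a coarse summary. A modest change in PR, QRS, QT or QTcF can differ between arms while every tracing is still read as normal, and only a by-arm summary of the intervals would show it. The protocol planned that summary, and the SAP withdraws it for a named safety outcome without saying why.

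Protocol 5.2.4 reports no ECG concern from phase I. Protocol 1.3 shows that this experience was in healthy subjects, with repeated dosing for 10 days. Here post-ACS patients are dosed for up to 12 weeks (84 days).

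The shift table has a separate weakness. Because it looks only at the last on-treatment ECG, an abnormal rating at Visit 3 or Visit 4 that has cleared by the last visit leaves no trace in it. In SAP 5.2 the haematology and chemistry shifts were moved from end of treatment to the worst on-treatment value; the ECG shift was not.

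**Working it through.** There is no planned figure to reproduce. The check compares the texts and counts what the outputs cover.

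**1. Interval coverage.** Six measures are recorded (protocol 5.2.4.1). RR and heart rate are largely covered by pulse in the vital signs table, which leaves 6 − 2 = 4: PR, QRS, QT and QTcF. SAP output section 14.3.8 has five tables: vital signs, physical examination, body weight and BMI, and two ECG rating shifts, one per cohort. None reports an interval. SAP 7.1 says in general terms that safety variables are summarised by arm and visit as appropriate, but the specific statement in SAP 5.2 and the output list override it for ECG.

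**2. ECGs that can enter the shift table.** The protocol plans about 138 patients, about 100 of them on 12 weeks, so about 38 on 4 weeks. Scheduled on-treatment ECGs after baseline are at Visits 3, 4 and 4c (12-week cohort) or Visits 3 and 4 (4-week cohort).

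- Scheduled: 100 × 3 + 38 × 2 = 376
- Used, one per patient: 138
- Not used: 376 − 138 = 238, and 238/376 = 63%

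By cohort, the shift uses 1 of 3 or 1 of 2. Counts are before dropout and missed visits.

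**3. By-arm route left for each kind of finding.**

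| Finding | By-arm route |
|---|---|
| Rated abnormal at last on-treatment ECG | Shift table |
| Earlier, resolved, clinically significant | Can be recorded as an adverse event (protocol 5.2.4, SAP 6.6.4), so can reach the adverse event tables |
| Earlier, resolved, not clinically significant | None; listed only |
| Interval change on an ECG rated normal | None; SAP 8.8.4 lists abnormal findings only |

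**4. What interval tables would show.** In the order of assessments (protocol 4.1, repeated in SAP 6.1), ECG is step 2 and study drug intake is step 5. Scheduled on-treatment ECGs are therefore pre-dose, and the summaries would mainly reflect trough or sustained effects.

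**5. Rating levels.** SAP 6.6.4 gives four levels, but plain abnormal overlaps the two graded abnormal levels. A worst-value rule needs an order that these levels do not supply.

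**6. Hy's-law table (minor).** On-treatment laboratory values end 7 days after last dose (SAP 6.6.3). Visit 5 falls at 28 ± 4 days, that is 24 to 32 days after last dose, or 17 to 25 days past that limit. Three illustrative patients with last dose on day 84:

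| Pattern | Meets definition | Falls in table cell |
|---|---|---|
| Bilirubin ≥2×ULN day 14, ALT ≥3×ULN only day 84 | No | Yes |
| ALT ≥3×ULN day 84, bilirubin ≥2×ULN first at Visit 5 | Yes | No |
| Both on day 28 | Yes | Yes |

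The table is narrower than the definition on time and looser on order.

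**The case against.** The strongest reply is that the ECG change is openly declared, that the protocol leaves analysis detail to the SAP, and that these are safety ECGs read in real time by experienced readers, with digital files kept for adjudication. All of that is true, so this is not a hidden contradiction. But declaring a change neither explains it nor restores the analysis, and reading tracings one by one cannot show a difference between arms.

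Other replies limit the point:

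- A reader might infer that early, transient ECG abnormalities vanish from the comparison. The documents do not support that for clinically significant ones, which can be recorded as adverse events at any visit. The 63% measures table coverage; it is not a share of lost safety findings.
- A reader might infer that interval tables would reveal effects near peak exposure. Pre-dose timing rules that out for scheduled ECGs, and no SD is given from which to judge what difference could be detected.
- A reader might infer that a firm commitment to outlier counts was dropped. Protocol 8.5.3 makes categorical outliers optional, and it is unclear whether its phrase on markedly abnormal values refers to ECG at all.
- The protocol specifies no worst-value ECG shift, and its laboratory shifts ran to end of treatment. A last-value shift is therefore defensible, and the worst-value shift is an addition.
- A reader might infer that Hy's-law cases would be missed. They would not: protocol Appendix D requires each potential case to be reported as an SAE, SAE tables cover the off-treatment phase, and the cross-tables are correctly titled as on-treatment maxima.

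**Conclusion.** The point holds for the intervals. Four of the six recorded ECG measures lose the by-arm summary that the protocol planned, with no reason given, and none of the five relevant tables replaces it. It holds in a limited form for the shift table: what lacks a by-arm count is earlier abnormal ratings that resolved and were not clinically significant. This is a reporting gap in a stated safety outcome. Nothing in the documents shows that an ECG effect exists or is being concealed.

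The counts assume the planned cohort sizes of about 100 and 38 and full attendance. The ease of repair assumes that the intervals are in the study database, which is inferred. Protocol 5.2.4.1 says they are recorded, and SAP 5.2 says explicitly when other variables (serology, FSH, LH) are not in the CRF but does not say so for ECG intervals. Against that, SAP 6.6.4 describes only the rating.

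The Hy's-law mismatch is a matter of alignment and labelling only.

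**What to change.** 1. Confirm that PR, QRS, QT and QTcF are in the study database. If they are, restore descriptive summaries of value and change from baseline, by visit and arm, with a note that scheduled ECGs are pre-dose. If they are not, say so in SAP 5.2 as the reason for the change and decide whether to extract them from the stored digital files.
2. Add a shift from baseline to worst on-treatment overall rating, by arm, beside the last-value shift, using an ordered set of rating levels that do not overlap.
3. Optionally, add by-arm outlier counts. The limits would have to be written into the SAP, since neither document gives them.
4. For Hy's law, either add a post-treatment row through Visit 5 and flag patients who meet the order rule, or label the table as an on-treatment screen.

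The cost is a few descriptive tables, with no new assessments and no effect on type I error. It rises only if the intervals have to be extracted from the source files.
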